## 11.4 Other Safety Measures

### 11.4.1 Immunogenicity

The number and percentage of subjects with a positive immunogenicity test (presence of binding antibodies to CSL346) at any time (Weeks 4, 8, and 16) during treatment and follow-up period will be summarized by treatment group, including a combined CSL346 treatment group. A treatment comparison of combined CSL346 treatment group vs. placebo treatment group will be done by using Fisher's Exact Test.

A by-subject listing for immunogenicity will be provided.

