An overview of identified and potential risks and planned risk mitigation in this phase 2a study is provided in Table 1.

Table 1 Risks and Risk Mitigation

Risk	Potential/ Identified	Source	Risk Mitigation
Injection site reactions	Identified	CSL346_1001 data on file	
 Assessment at study visits Guidance for managing local intolerance
Hypersensitivity / anaphylaxis and infusion reactions; antibody formation	Potential	Class effect of humanized proteins	
 Standard measures Measurement of baseline, mid-, and end of study anti-CSL346 antibody
Weight gain	Potential	Knock-out mouse model [Hagberg et al, 2010]	
 Monitor at study visits
Congenital disorders	Potential	Knock-out mouse model [Bellomo et al, 2000] Preclinical study in quails [Tomanek et al, 2006]	
 Inclusion / exclusion criteria Contraception requirements Pregnancy testing Nonclinical studies in later phases
Renal: acute reversible effect on GFR and / or chronic kidney injury	Potential	Theoretical risk due to VEGF-A modulation [Kamarzarian et al, 2018; Izzedine et al, 2010]	
 Inclusion / exclusion criteria Staged approach for enrollment of subjects with moderate renal impairment Frequent monitoring in first 4 weeks of treatment Measure SCr and evaluate albuminuria at each visit Guidance for managing increases in SCr and albuminuria

Risk	Potential/Identified	Source	Risk Mitigation
Cardiac: myocardial dysfunction with chronic dosing	Potential	Knock-out mouse model [Bellomo et al, 2000] Streptozotocin model [Lal et al, 2017] Theoretical risk due to VEGF-A modulation [Touyz et al, 2018]	
 Exclusion criteria, including baseline assessment of LVEF by ECHO Treatment with SOC Baseline and periodic ECG, BNP, and troponin levels Guidance for managing increases in troponin levels
Increased BP	Potential	Theoretical risk due to VEGF-A modulation [Touyz et al, 2018]	
 Exclusion criteria BP measurement Guidance for managing increases in BP

BP = blood pressure; BNP = b-type natriuretic peptide; ECG = electrocardiogram; ECHO = echocardiogram; GFR = glomerular filtration rate; LVEF = left ventricular ejection fraction; SCr = serum creatinine; SOC = standard of care; VEGF = vascular endothelial growth factor.

2 Study Objectives and Endpoints

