2.2.2 Secondary Endpoints

Secondary Objective	Endpoint	Summary Measure
1	Treatment-emergent adverse events, including adverse events of special interest (AESIs) from the time of first dose of the IP through End of Study (EOS)	Number and percentage of subjects overall, by severity, by relatedness, by seriousness, and by action (ie, IP discontinuation)
2	Observed value and change from Baseline in SCr and eGFR through EOS	Mean (SD)
3	Observed value and change from Baseline in systolic and diastolic blood pressure (SBP and DBP) through EOS	Mean (SD)
4	CSL346 serum PK: 
 • Maximum concentration (C_{max}) after IV loading dose • Time to reach C_{max} in serum (T_{max}) after IV loading dose • C_{max} after first SC dose • T_{max} in serum after first SC dose • Area under the concentration-time curve in first dosing interval ($AUC_{0-\tau}$) • Trough concentration (C_{trough}) after each dose 	Mean (SD), coefficient of variation (%CV) and geometric mean for all parameters except T_{max} ; Median (minimum, maximum) for T_{max}
5	Presence of anti-drug antibody at Week 4 (Visit 7), Week 8 (Visit 8), and Week 16 (Visit 10)	Number and percentage of subjects with positive result (with reciprocal titer)

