8.6.4 Treatment

8.6.4.1 Treatment Visit 4 (Day 1)

8.6.4.1.1 Before Administration of IP

Subjects who complete all Screening assessments and who satisfy the randomization criteria will be enrolled into the study and randomized. After randomization, the following procedures are to be conducted and documented at Visit 4 before administration of IP:

- Confirm and document that the subject conforms with randomization criterion for BP
- Perform serum or urine pregnancy test (FCBP only)
- Perform abbreviated physical examination
- Measure vital signs (BP in triplicate)
- Measure weight
- Perform 12-lead ECG (triplicate)
- Collect blood samples for the following:
 - Standard hematology and biochemistry testing
 - Troponin-I and BNP
 - HbA1c
 - Immunogenicity
 - Biomarker analysis
- Collect blood sample for PK before dosing
- Collect urine samples for the following:
 - FMV (for Days -2, -1, and 1)
 - Morning midstream
 - Standard urinalysis
- Collect information on AEs
- Collect information on concomitant therapies

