10.3.7 Other Analyses

Secondary Endpoint

The number of subjects with a positive immunogenicity test at any time posttreatment will be counted and compared between treatments with Fisher's Exact Test. The comparison will be of CSL346 (8 mg/kg and 16 mg/kg pooled) versus placebo. This analysis will be performed on the Safety Analysis Set.

Exploratory Endpoints

Exploratory endpoints will employ a model similar to the primary endpoint. The analysis for these continuous endpoints is an MMRM analysis of change from Baseline to each postbaseline measurement. The model will include treatment, stratification related to the concomitant use of SGLT2 inhibitors, visit (as a categorical factor), and interactions between visit and each of the other model terms, as well as the corresponding baseline measurement as a covariate. Exploratory urinary biomarkers will be normalized to creatinine level for analysis and reporting. Treatment comparisons of interest will be similar to that of the primary endpoint. These analyses will be performed on the PD Analysis Set.

The number of subjects who regress from macroalbuminuria to microalbuminuria or normoalbuminuria, or from microalbuminuria to normoalbuminuria at Week 16 will be counted and compared between treatments using Fisher's Exact Test. The comparison will be of CSL346 (8 mg/kg and 16 mg/kg pooled) versus placebo.

11 Quality Assurance

The study may be subject to an audit by CSL, an authorized representative(s) of CSL and / or inspections by an authorized health authority (eg, US Food and Drug Administration). Health authorities may request access to all study documentation, including source documents for

inspection and copying, in keeping with local regulations. CSL will notify the Investigator of any upcoming audit / inspection.

In the event of an audit, all pertinent study-related documentation must be made available to the auditor(s). If an audit or inspection occurs, the Investigator at each study site will permit the auditor / inspector direct access to all relevant documents and allocate their time as well as the time of relevant staff to discuss the findings and any relevant issues.

12 Regulatory and Ethics Considerations

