### **8.2.3 Baseline Definition**

Baseline is defined as the most recent, non-missing value before the first IP administration (including unscheduled visits) for all assessments unless otherwise stated. In case of an assessment at the same date as the first IP administration (and only the date for that assessment is available) it will be assumed the assessment was done before IP administration.

For the purposes of the analysis of albumin creatinine ratio, baseline will be defined as the geometric mean of the 6 values obtained before treatment (3 values from Visit 3 and 3 values immediately before treatment at Visit 4). If fewer than 6 values are available, the geometric mean of all the available values will be used for baseline.

Baseline for blood pressure will be the mean of the three values (or all available if fewer than three) collected immediately before the IV loading dose.

Baseline for serum creatinine will be an average of the two samples collected prior to first IP administration (Visit 3 and Visit 4). Baseline eGFR will be calculated based on the baseline

serum creatinine. These calculated baseline eGFR values will be used to define eGFR categories and covariates in statistical analyses.

For soluble tumor necrosis factor receptor 1 (sTNFR1), exploratory circulating and urinary markers, the baseline value will be an average of the two samples collected prior to first IP administration (Visit 3 and Visit 4). [Note: Exploratory circulating biomarkers are defined in [Section 4.1.4](#) as biomarkers of lipid metabolism including but not limited to circulating total cholesterol, triglycerides, high density lipoproteins (HDL), low density lipoproteins (LDL), glycerol, non-esterified fatty acids (NEFA), and ketones. Urinary markers are defined in [Section 10.3](#) as VEGF-A, soluble VEGF receptor 1 (VEGF-R1), kidney injury molecule-1 (KIM-1), neutrophil gelatinase-associated lipocalin (NGAL), clusterin, monocyte chemoattractant protein-1 (MCP-1) and epidermal growth factor (EGF).]

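### The immunogenicity count and Fisher's test do not condition on the pre-dose Day 1 antibody result, which costs precision if any subjects are already reactive

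*SAP*

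**What the plan says.** Protocol 10.3.7 plans to count subjects "with a positive immunogenicity test at any time posttreatment" and to compare pooled CSL346 with placebo by Fisher's Exact Test. SAP 11.4.1 keeps this rule and names the visits: a "positive immunogenicity test (presence of binding antibodies to CSL346) at any time (Weeks 4, 8, and 16"). It adds that "A treatment comparison of combined CSL346 treatment group vs. placebo treatment group will be done", again with Fisher's test, and that a by-subject listing will be produced. Neither section mentions Day 1 status.

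A Day 1 sample is nevertheless taken. The Schedule of Assessments has immunogenicity at Visit 4. Protocol 8.6.4.1.1 puts it among the bloods drawn under the instruction that "the following procedures are to be conducted and documented at Visit 4 before administration of IP". The risk table in Protocol 1.4 gives "Measurement of baseline, mid-, and end of study anti-CSL346 antibody" as a mitigation for hypersensitivity and antibody formation. SAP 8.2.3 has a general rule that could be applied: "Baseline is defined as the most recent, non-missing value before the first IP administration".

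The endpoint in Protocol 2.2.2 and SAP Table 1 is presence of antibody at Weeks 4, 8 and 16, summarised as "Number and percentage of subjects with positive result (with reciprocal titer"). The assay is tiered, with screening, specificity and titration steps (footnote to Protocol Table 6).

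**The concern.** The secondary objective is to evaluate the immunogenicity of CSL346, which is naturally read as asking whether the drug induces or boosts antibodies. Under the planned rule, a subject who was reactive before dosing and stays reactive counts the same as one who converts after dosing. Such subjects appear in both arms. They add background to the only formal immunogenicity comparison and raise the percentage that a reader will attribute to CSL346.

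The SAP treats its other safety data differently. Adverse events are classified as treatment-emergent relative to first dose (11.2), and laboratory values, vital signs and ECG are summarised as change from baseline (11.3, 11.4.2, 11.4.3). Antibody status also has a baseline sample, but that sample has no part in the summary or the test.

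**Working it through.** **Plan's own figure.** The documents state no rate, power, alpha or sidedness for the immunogenicity comparison. The only usable input is the group size, 50 versus 50, from the primary ACR sizing (Protocol 10.1, SAP 4.4). That sizing reproduces: 2 × (1.2816 + 1.0364)² × 0.65² / 0.3147² = 45.8, so 46 per arm against the stated 47 (94 in total), and 94 / 0.94 = 100.

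**Assumed inputs (not in the documents).**
- b: proportion positive on Day 1, the same in both arms, who stay positive after dosing.
- t: proportion of Day 1 negatives induced by CSL346.
- s: proportion of Day 1 negatives converting spontaneously in either arm, independently of induction.

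**Expected proportions.** Let c = 1 − (1 − t)(1 − s).
- As written: b + (1 − b)c on CSL346 versus b + (1 − b)s on placebo.
- Treatment-emergent: (1 − b)c versus (1 − b)s.

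The absolute difference, (1 − b)(c − s), is the same under both rules. What differs is the background on which it sits. With b = 5%, t = 15%, s = 0, the as-written rates are 0.05 + 0.95 × 0.15 = 19.25% versus 5%. The treatment-emergent rates are 14.25% versus 0%. Both differences are 14.25 points.

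**Exact power of Fisher's test.** Binomial probabilities are summed over the rejection region, 50 versus 50. The first seven rows are two-sided 5%; the last is one-sided 0.10.

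| b | t | s | As written | Treatment-emergent |
|---|---|---|---|---|
| 0% | 15% | 0% | 78% | 78% |
| 2% | 15% | 0% | 61% | 76% |
| 5% | 15% | 0% | 47% | 74% |
| 10% | 15% | 0% | 34% | 68% |
| 5% | 15% | 2% | 41% | 58% |
| 5% | 15% | 4% | 36% | 47% |
| 5% | 5% | 0% | 6% | 3% |
| 5% (one-sided 0.10) | 15% | 0% | 76% | 94% |

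**Validity under the null.** With no induction and no spontaneous conversion, the as-written two-sided 5% test rejects in 0.7% of trials at b = 5% and 1.8% at b = 10%. It is conservative, not inflated.

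**Worked example.** Take 3 pre-existing positives per arm and 6 new positives on CSL346. The planned rule gives 9/50 versus 3/50 (18% versus 6%), two-sided p = 0.121. The treatment-emergent rule gives 6/50 versus 0/50 (12% versus 0%), p = 0.027. Both show a 12-point difference. At two-sided 5%, significance needs 6 positives against 0, but 11 against 3.

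These calculations count induced cases only. The recommended rule also counts boosted cases (Day 1 positive with a titre rise), which are not modelled because the documents give no basis for a rate.

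**The case against.** The strongest reply is that placebo is a concurrent randomised control. Pre-existing positives are balanced in expectation, the expected absolute difference is unchanged, and the test stays valid. All of that stands. A reader might infer that the comparison is biased; it is not.

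A reader might also infer that titres are thrown away or that the Day 1 result is never seen. The documents do not support either reading. Reciprocal titre is part of the planned summary measure, and SAP 8.2.5 puts data from all assessments into listings, so Day 1 status should be visible subject by subject. What is missing is narrower: a summary or test that uses Day 1 status, and a definition of titre rise. Table shells are in a separate document and could add a Day 1 tabulation, but the counting rule is set in the SAP text.

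The endpoint is presence of antibody, and the planned percentage reports that correctly. It overstates only if read as treatment-emergent incidence, although the stated objective invites that reading.

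The size of the loss is uncertain. The specificity step limits false positives, though it does not remove true pre-existing binding antibody. SAP 16.9 describes the study's treatment comparisons as one-sided, and power is higher under both rules at one-sided 0.10; its table does not list immunogenicity, however. Finally, little depends on this test. It has no power target, and antibody status is not a stopping criterion in Protocol 3.7.

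**Conclusion.** The point holds as an inexpensive improvement, not as an error that threatens a conclusion. The planned count and test do not condition on Day 1 antibody status. For the objective of evaluating CSL346's immunogenicity, a treatment-emergent count is the better measure, and its samples are already collected.

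The cost of leaving the rule alone is lower precision and per-arm percentages that overstate treatment-emergent incidence. At 15% induced, two-sided 5% and no spontaneous conversion, the power lost is nil with no pre-existing positives, about 15 points at 2%, 27 at 5% and 34 at 10%. At 5% pre-existing it falls to about 17 or 11 points if 2% or 4% convert spontaneously in both arms. At one-sided 0.10 with 5% pre-existing and no spontaneous conversion it is about 18 points. If only 5% are induced, neither rule has useful power and there is no gain. All of these rest on assumed rates and on Day 1 positives remaining positive after dosing. The primary ACR analysis and sample size are unaffected.

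**What to change.** In SAP 11.4.1:
- Run Fisher's test on treatment-emergent positives: negative on Day 1 and positive at Week 4, 8 or 16, or positive on Day 1 with a titre rise above a stated threshold. Fix the threshold before unblinding; the planned unblinding is at the Week 16 interim analysis. A threshold chosen later should be labelled post hoc.
- Tabulate Day 1 positives by arm.
- Keep any-post-dose positivity by arm as a descriptive summary of the protocol endpoint.
- State how a subject with a missing Day 1 sample is handled, and give the test's alpha and sidedness.

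Because Protocol 10.3.7 states the current rule, list the change in SAP section 5. The cost is a short paragraph of specification and one added table. No new samples or visits are needed.

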## 11.4.2 Vital Signs

The vital signs will be summarized by visit and by the three randomized treatment groups and a combined CSL346 treatment group. The summaries will be provided for the analysis population as described in [Section 11](#).

The following summaries will be provided for systolic and diastolic blood pressure, heart rate, body temperature and body weight:

- Values of vital signs by scheduled visit,
- Change from baseline by scheduled visit.

Vital signs will be assessed as a triplicate measurement. For purpose of analysis the mean value of such triplicate parameter assessments will be used.

Vital sign values of potential clinical importance will be determined by using the criteria detailed in Table 4. The number and percentage of subjects with vital signs of potential clinical importance will be summarized by visit and at any time for the three randomized treatment groups and a combined CSL346 treatment group.

A by-subject listing of all vital sign data (scheduled and unscheduled visits) will also be presented. The listing will include a flag for values of potential clinical importance.

**Table 4 Vital Signs of Potential Clinical Importance**

Vital Sign Parameter	Potential Clinical Importance (PCI) Range	Unit
Hypertensive AESI – Flag for crisis (definitions are the same; clinical presentation defines a crisis)	SBP $\geq$ 180 mmHg and/or DBP $\geq$ 120 mmHg OR an increase from Baseline in either SBP or DBP $\geq$ 20 mmHg and SBP/DBP greater than 160/105 mmHg	mmHg
DBP	<45	mmHg
SBP	<85	mmHg
Heart rate	<40 or >110	bpm

## 11.4.3 ECG

The ECG parameter (PR interval, QRS duration, QT interval, QTcF, QTcB, heart rate) and their changes from baseline will be summarized by visit and by the three randomized treatment groups and a combined CSL346 treatment group. The summaries will be provided for the analysis population as described in [Section 11](#).

ECG assessments will be done as a triplicate measurement. For purpose of analysis the mean value of such triplicate parameter assessments will be used.

For QTcF, PR interval, QRS interval and heart rate, values of potential clinical importance will be determined by using the criteria detailed in Table 5. The number and percentage of subjects with those values of potential clinical importance will be summarized by visit and at any time for the three randomized treatment groups and a combined CSL346 treatment group. Subgroup summaries will also be provided by gender. The overall interpretation of ECG will be summarized at the same time points and treatment groups.

**Table 5 ECG Parameters of Potential Clinical Importance**

ECG Parameter	Potential Clinical Importance (PCI) Range	Unit
QTcF Interval	>450 OR <500 or $\geq$ 500 OR $\geq$ 500 OR increase from Baseline $\geq$ 60 or increase from Baseline between >30 and <60	msec
Absolute PR Interval	<120 or >210	msec
Absolute QRS Interval	<75 or >110 or >120	msec
Heart rate	<50 or $\geq$ 120	bpm

A by-subject listing of all ECG data (scheduled and unscheduled visits) will also be presented. The listing will include a flag for values of potential clinical importance.

## 12 Pharmacokinetic Analyses

The PK analysis will be performed using the PK Analysis Set.

All non-compartmental analyses are to be performed according to CSL SOP PK-GDL-01 and will be performed by CSL Behring Clinical Pharmacology & Pharmacometrics by using WinNonlin® version 8.1 or later. Alternatively CSL Behring may contracting a Clinical Research Organisation to derive the PK parameter.

After data base lock, CSL Behring Clinical Pharmacology & Pharmacometrics will produce all SDTM domains needed for the PK analysis (serum PK analysis). The PC domain containing the CSL346 concentrations, nominal blood sampling times, actual sampling time relative to the start of the dosing, and actual dosing and the PP domain containing the PK parameters will be provided. Any CSL346 serum concentrations which will have been excluded from the derivation of the PK parameters will be flagged in the data.

Parexel will produce the TFLs for the CSL346 serum concentrations and the PK parameters as specified below.

Population PK analyses will be performed according to the Modeling and Simulation Analysis Plan and reported separately.

## 12.1 Drug Concentration Measures

The handling and imputation of below limit of quantification (BLQ) values for PK parameter derivation is described in (1), (2), (3), and (4). The imputation rules below will be used for summary statistics of CSL346 serum concentrations. The summaries will be given by planned time point.

- The sampling time of pre-dose samples relative to start of the dose infusion will be treated as zero;
- Concentration values below BLQ in pre-dose samples and in samples taken before the time of the first quantifiable concentration will be treated as zero;
- Post-dose BLQ concentrations flanked by quantifiable concentrations will be set to missing;
- Post-dose BLQ concentrations after the last quantifiable point will be set to missing for summary statistics of serum concentrations;
- The mean/median value at a time point where one or more samples have BLQ values will be reported (in tabular or graphical fashion) even if the mean/median value is BLQ of the assay;
- Zero mean or median values will be included in summary tables.

The lower limit of quantification for CSL346 in serum is 80 ng/mL and in urine it is 80 ng/mL. Concentrations that are below BLQ should be reported as “< LLOQ” in listings.

It should be noted that a high proportion of BLQ values may affect the summary statistics; if more than 50% of the values are imputed (i.e. BLQ), then the summary statistics (mean, SD, median, quartiles) will not be displayed.

Summary statistics for concentration-time data will include the percentage of BLQ values relative to the total N

$$\%BLQ = 100 * (\text{number of subjects who have BLQ values} / \text{total number of subjects})$$

at each time point.

Descriptive statistics will be provided as outlined in [Section 7](#), and in addition the CV% (CV% = 100\* standard deviation / mean) and geometric mean.

Individual CSL346 serum concentration plots will be plotted versus actual sampling time from predose on Day 1 through predose on Day 29. Each plot will have a graph on the untransformed scale (i.e. a linear plot) and one plot on the log transformed scale (i.e. log-linear plot).

Plots for mean ( $\pm$  SD) CSL346 serum concentrations (on linear and on log-linear scales) versus nominal (planned) time will be provided from predose on Day 1 through predose on Day 29. All treatment groups will be overlaid for the mean plot. If more than 50% of the individual values are BLQ, the mean and SD will be set to missing in the plots.

Additionally, a box and whisker plot on nominal sampling time for serum concentrations at predose time points on Days 29, 57, 85, as well as concentrations on Days 113 and 169 will be provided. All treatment groups will be displayed in one plot.

Serum concentrations excluded from the derivation of the PK parameters will also be excluded from the summary statistics and the mean plots. A footnote will indicate if serum concentrations have been excluded from the analysis.

A by-subject listing of CSL346 serum concentrations with the concentrations flagged that have been excluded from the derivation of the PK parameters based on the PK Analysis Set will support the summaries.

Urine concentration of CSL346 will be summarized by nominal time point using the same summary statistics as for serum concentration and a by-subject listing will be provided.

